1 INTRODUCTION

1.1 Background

End-stage renal disease (ESRD) is a condition in which there is an irreversible decline in kidney function severe enough to be fatal in the absence of dialysis treatment or kidney transplantation. Reduction in, or absence of, kidney function leads to a host of maladaptive changes including fluid retention (extracellular volume overload), anemia, disturbances of bone and mineral metabolism, dyslipidemia, and protein energy malnutrition (Heye 2012). The incidence of end-stage renal disease in the United States increases by 5% per year, largely due to the growing prevalence of hypertension and diabetes. Currently in the US over 661,000 individuals have been diagnosed with ESRD, and of these, approximately 468,000 are receiving hemodialysis. The average cost of dialysis is \$89,000 per patient, per year, for a total cost to the US medical system of approximately \$42 billion annually, of which \$34 billion is absorbed by Medicare. Approximately 1% of the Medicare population undergoes chronic dialysis, but accounts for 7% of the Medicare budget (USRDS 2015).

Despite improvements over the past 50 years since hemodialysis became available, the mortality rate for patients with ESRD undergoing hemodialysis is 20-25% at one year, with a 5 year survival of only 35% (USRDS 2015). In part, this poor prognosis is due to the compounded impact of concurrent health conditions. Three-quarters of dialysis patients have 5 or more comorbidities, and 90% have cardiovascular disease (USRDS 2005). Hemodialysis access site and venous outflow circuit dysfunction are directly related to morbidity in this population. Inadequate dialysis can lead to cardiopulmonary decompensation, life-threatening electrolyte imbalances, and a multitude of other physiologic complications (Heye 2012). Thus, the ability to effectively complete hemodialysis treatments is critical to improving outcomes.

Vascular access for hemodialysis is achieved via arteriovenous fistula (AVF), arteriovenous graft (AVG) or central venous catheter (CVC). The National Kidney Foundation Kidney Disease Outcomes Quality DCO20-036_09OCT2020

Confidential

Page 3 of 34

Initiatives (KDOQI 2006) recommends AVF (direct surgical connection of artery to vein) as the first choice for vascular access due to longer period of patency, improved durability, and low infection rate. AVF site location in order of preference, is forearm/radiocephalic, elbow/brachiocephalic, and arm/brachiobasilic (Santoro 2014). An access in the wrist area is considered the gold standard since it is relatively simple to create, has a low incidence of complications, and if abandonment becomes necessary, it allows for more proximal future access (VAWG 2006). AVFs must be planned a minimum of a month in advance, and may take 3 months or longer to mature. This lead time can make AVFs unsuitable for patients with near term dialysis needs.

Arteriovenous grafts (AVGs) consist of a synthetic interposition between an artery and a vein and are the second choice for dialysis access. Although patency is generally of shorter duration than AVFs, AVGs may be used when autogenous options have been exhausted, or as a first line choice in patients whose superficial veins are deep in subcutaneous tissue, or those with extreme vascular fragility (Santoro 2014). Central venous catheter access is considered the third ranked choice because of the high risk of thrombosis and infection (KDOQI 2006). Use is predominantly in patients with urgent need of dialysis in which there is insufficient time to establish an AVF or AVG, or when other accesses have become dysfunctional. Avoidance of CVC use is recommended whenever possible (Fistula First, 2018).

Vascular access dysfunction, defined as low or no-flow fistulae and grafts, accounts for 20% of all hospitalizations in ESRD (Feldman 1996). Primary complications of AVFs are failure to mature and venous stenosis followed by thrombosis (Roy-Chaudhury 2006). Time from surgery to use is shorter for AVGs, but rates of stenosis, thrombosis and infection are higher (NIDDK). Stenoses for both these forms of vascular access occur at or near the anastomotic region, and involve neointimal hyperplasia, adverse vascular remodeling, and thrombosis. Although the mechanisms responsible are complex and not completely understood, factors include flow turbulence, inflammation, and a prothrombotic

environment from endothelial damage (Ocak 2013). The result to the patient is access dysfunction causing reduced blood flow, edema, pain, and neurological compromise.

Treatment of hemodialysis access site stenoses to restore adequate flow and prolong the viability of the anastomosis is performed by surgery or catheter-based interventions such as percutaneous transluminal angioplasty (PTA) or placement of a stent-graft. KDOQI guidelines recommend balloon angioplasty or surgical revision if there is a >50% decrease in luminal diameter and abnormal physical findings, or decreasing intra-anastomosis flow, or elevated static pressure within the anastomosis. If PTA fails, KDOQI guidelines state that stents may be useful (KDOQI 2006).

1.2 Stent Grafts For Access Circuit Revision

Four prospective, multicenter, randomized studies conducted by Haskal, Vesely (2010; 2016), and Falk compared the performance of stent grafts (SG), percutaneous transluminal angioplasty (PTA), and bare metal stents (BMS) for treating failing or dysfunctional AVFs or AVGs. All four clinical trials demonstrated that stent grafts provided superior patency and fewer reinterventions compared to balloon angioplasty alone (Haskal 2010; Haskal 2016; Vesely 2016; Falk 2016).

In the pivotal trial of the FLAIR® Endovascular Stent Graft (Bard, Tempe AZ) 190 subjects with dialysis access graft venous anastomotic stenosis were randomized at 13 sites to PTA alone, or PTA with placement of a nitinol stent covered in carbon impregnated expanded polytetrafluoroethylene (ePTFE). The results showed statistically significantly better treatment area primary patency (TAPP) for stent grafts (SG) compared to PTA alone.

At 6 months, TAPP and access circuit primary patency (ACPP) were statistically significantly better for SG than PTA (TAPP: 51% vs 23%, p<.001) (ACPP: 38% vs 20%, p=.008). Freedom from reintervention at 6 months was also better in the stent graft group (32% vs 16%, p=.03), with incidence of restenosis being higher in the PTA group (78% vs 28%, p<.001) (Haskal 2010).

Haskal and colleagues conducted a second prospective, randomized study comparing outcomes from a stent graft (FLAIR Endovascular Stent Graft) to PTA, the RENOVA trial. This study included 270 patients with stenosis at the graft-vein anastomosis of their AVG's at 28 sites. At 12 months, the results showed statistically significantly better TAPP for the SG compared to PTA alone (47.6% vs 24.8%, $p < .001$). For the same time period, ACPP and index of patency function (IPF) was also better in the stent graft group (ACPP: 24% vs PTA 11%, $p = .007$) (IPF: 5.2 months/intervention vs 4.4 months/intervention, $p = .009$) (Haskal 2016).

At 24 months, the results continued to be statistically significantly better for the SG compared to PTA alone (TAPP: 26.9% vs 13.5%, $p < .001$) (ACPP: 9.5% vs 5.5%, $p = .01$) (IPF: 7.1 months/intervention vs 5.3 months/intervention). The estimated number of reinterventions before graft abandonment was 3.4 for SG subjects versus 4.3 for PTA subjects. There were no statistically significant differences in adverse events ($p > .05$), except rates for restenosis requiring reintervention at 82.6% in PTA subjects vs 63.0% in SG subjects ($p < .001$) (Haskal 2016).

The REVISE study was a multi-center prospective randomized trial in which 293 subjects with in-stent stenosis of the AVG venous anastomosis were randomized to receive PTA alone or PTA plus placement of the GORE® VIABAHN® Endoprosthesis with Heparin Bioactive Surface (Gore, Flagstaff AZ). The REVISE study demonstrated that the use of the VIABAHN device to treat venous anastomotic stenosis in stenosed and/or failing access grafts provided superior patency and fewer reinterventions when compared to balloon angioplasty alone (Vesely 2016). The REVISE study is the first prospective study of stent grafts for failing AVGs that included subjects with either stenotic or thrombotic hemodialysis access.

Study subjects treated with a VIABAHN device had statistically significantly better primary patency rates of the target lesion at 6 months when compared to PTA alone (51.6% vs 34.2%, $p=.006$). Subjects treated with a VIABAHN stent graft also had better primary patency of the entire arteriovenous access

circuit at 6 months (41.5% vs 28.4%, p=.035). At 24 months, there was no statistically significant difference between SG and PTA groups in the percentage of subjects with a secondary stenosis (24% vs 21%, p=.58) (Vesely 2016).

The RESCUE study was a prospective, multicenter, randomized, concurrently controlled clinical trial designed to assess the performance of the FLUENCY® PLUS Endovascular Stent Graft (Bard, Tempe AZ) compared to PTA alone in the treatment of in-stent restenosis in the access circuit of subjects receiving hemodialysis with an AV graft or native fistula (Falk 2016).

This study showed that the stent group results were superior to PTA with respect to 6-month access circuit primary patency (ACPP) and was non- inferior to PTA with respect to safety. ACPP at 6 months was significantly higher in SG than the PTA group (18.6% vs 4.5%, p < .001). Freedom from safety events at 30 days was comparable (SG: 96.9% vs PTA: 96.4%, $\delta = 0.075$, p =.003 for non-inferiority). Treatment area primary patency (TAPP) was superior for (SG) at 6 months (66.4% vs 12.3%, p < .001). Unlike previous studies that compared SG to PTA to revise dialysis accesses, the RESCUE study included treatment of restenosis in both the peripheral and central veins (Falk 2016).

ACPP at 24 months was not statistically significantly different between the SG and PTA group (0.9 vs 0.8, p=ns) nor were they statistically significantly different for lesions treated in the central vein, (SG: 1.1 vs PTA: 0.0, p=ns), or peripheral vein (0.0 vs 2.0 p=ns). However, TAPP at 24 months was statistically significantly better in SG for lesions in both the central and peripheral veins (13.6 vs 4.3, p<.001) and (16.5 vs 1.7, p<.001), respectively (Falk 2016).

1.3 Thoracic Central Vein Obstruction (TCVO)

Thoracic Central Vein Obstruction (TCVO) is a common and major complication of hemodialysis and can be caused or exacerbated by pacemaker and automatic internal cardiac defibrillator (AICD) wires, peripherally inserted central catheters, and/or a history of central venous catheter use (Agarwal 2009).

This is thought to be due to trauma and the associated inflammatory response, resulting in the formation of thrombus, intimal hyperplasia and fibrotic response (Agarwal 2015). Clinical symptoms of TCVO include edema, tenderness, pain and erythema. Thoracic central venous obstruction can lead to aneurysmal dilation and tortuosity of the arteriovenous access and/or development of enlarged venous contralaterals which divert blood flow around the obstruction. This can result in decreased blood flow and recirculation at the access site and inadequate dialysis (Kundu 2009).

First line treatment for symptomatic TCVO is percutaneous transluminal angioplasty, but neointimal hyperplasia can progress due to damage to the vessel lumen from PTA, and stenosis has been shown to progress faster after intervention (Levit 2006). The mechanism of angioplasty involves cracking and fissuring the vessel intima which can accelerate intimal hyperplasia, and recurrent lesions after PTA have been demonstrated to have a higher proliferative index than the primary lesion (Chang 2004).

Central veins are more elastic and therefore more likely to recoil after PTA than the peripheral veins, with more than 50% of central lesions showing immediate recoil (Davidson 1991). For this reason, bare metal stents have been used to achieve acceptable technical results after PTA. KDOQI Vascular Access Guidelines recommend that PTA is the first-line treatment for stenosis in the access circuit. The guidelines also suggest stent placement as a treatment option for acute elastic recoil after PTA, when a stenosis recurs within 3 months, in subjects at increased risk for surgery, or following vessel rupture (KDOQI 2000).

Stent grafts have been used to treat TCVO, but most reports cite their use within larger randomized clinical trials or in small cohort studies. In a study by Jones and colleagues, VIABAHN stent grafts were placed in the central veins of 42 subjects with stenosis that did not respond to PTA. Primary patency rates at 3, 6, 12, and 24 months were 97%, 81%, 67%, and 45%, respectively. Primary assisted patency rates at 3, 6, 12, and 24 months were 100%, 100%, 80%, and 75%. This suggests that stent grafts placed

for the treatment of central venous stenosis are an effective way to maintain luminal patency if PTA fails (Jones 2011).

As further support, in the RESCUE study summarized earlier, a subset of 73 subjects (total study n = 275) with stenoses in the central vein (n=41), subclavian vein (n=30), brachiocephalic vein (n=1), and superior vena cava (n=1) demonstrated statistically significantly better primary patency in the treatment area at 24 months for the stent graft group vs PTA (13.6% vs 4.3%, p < .001).

To date there have been no large prospective randomized studies to investigate stent graft performance in the central veins.

Stent grafts used in central veins are the GORE VIABAHN, FLUENCY PLUS and the FLAIR Endovascular Stent Graft. Per these products' Instructions for Use, the VIABAHN stent graft is a flexible, self-expanding endoluminal endoprostheses consisting of an expanded polytetrafluoroethylene (ePTFE) lining with an external nitinol support extending along its entire length. The FLUENCY PLUS is a flexible self-expanding vascular prosthesis comprising ePTFE encapsulating a nitinol frame work, except for 2 mm at each of the flared stent graft ends with 4 radiopaque Tantulum markers. The inner lumen of the stent graft surface is carbon impregnated. The FLAIR Endovascular Stent Graft is a flexible, self-expanding endoprostheses comprising an expanded (ePTFE) encapsulating a nitinol stent framework. The nitinol stent, including distal and proximal ends, is encapsulated within the ePTFE and the inner lumen of the stent graft is carbon impregnated. The ePTFE outer wall of the stent graft, which contacts the AV access graft and native vein, contains cutouts which expose the nitinol stent.

1.4 The WRAPSODY Stent Graft

A series of 20 horizontal black bars of varying lengths, decreasing in length from top to bottom. The bars are evenly spaced and extend across the width of the frame.

2 STUDY OBJECTIVES

2.1 Primary Objectives

Safety

- Proportion of subjects without any localized or systemic safety events through 30 days that affect the access or venous outflow circuit and resulted in surgery, hospitalization, or death
 - Safety events in this calculation will not include venous outflow obstructions, which are captured in the calculation of Assisted Primary Patency of the target lesion, Assisted Primary Patency of the venous outflow circuit and Index of Patency Function

Effectiveness

- Proportion of subjects with Target Lesion Primary Patency at 30 days
 - Time to loss of Target Lesion Primary Patency is defined as the time interval of uninterrupted patency from initial study procedure to the next intervention performed on the target lesion or uncorrectable target lesion occlusion, whichever occurs first

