2.2 Secondary Objectives

- Proportion of subjects with Target Lesion Primary Patency at 3, 6 and 12 months
- Proportion of subjects with Assisted Primary Patency of the target lesion at 30 days, 3, 6 and 12 months
 - Time to loss of Assisted Primary Patency of the target lesion is defined as time following study procedure until uncorrectable target lesion occlusion
- Proportion of subjects with Primary Patency of the venous outflow circuit at 30 days, 3, 6, and 12months
 - Time to loss of Primary Patency of the venous outflow circuit is defined as the time following initial study procedure until the next venous outflow circuit intervention
- Proportion of subjects with Assisted Primary Patency of the venous outflow circuit at 30 days, 3, 6 and 12 months.

- Time to loss of Assisted Primary Patency of the venous outflow circuit is defined as the time following initial study procedure until complete access abandonment.
- Index of Patency Function at 3, 6 and 12 months, defined as time from initial study procedure to complete access abandonment divided by number of venous outflow circuit re-interventions to maintain hemodialysis
- Procedure or device related adverse events at 3, 6 and 12 months
- Clinical Success
 - The resumption of successful dialysis through existing access for at least one session following initial study procedure
- Anatomic Success
 - Less than 30% residual stenosis immediately following study procedure
- Procedural Success
 - The achievement of both clinical and anatomic success

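### Venous outflow obstructions that lead to surgery, hospitalization or death by day 30 are reported in no specified safety endpoint, and two of the three measures said to capture them miss corrected ones

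*Combined protocol and SAP*

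**What the plan says.** The primary safety endpoint (Sections 2.1, 4 and 9) is the proportion of subjects free, through 30 days, of safety events that affect the access or venous outflow circuit and result in surgery, hospitalization or death. An exclusion follows: "Safety events in this calculation will not include venous outflow obstructions, which are captured in the calculation of Assisted Primary Patency" of the target lesion. The sentence goes on to name Assisted Primary Patency of the venous outflow circuit and IPF. Section 7.1 gives the same reason for not treating these obstructions as AEs, and it defines an SAE as an AE that meets a seriousness criterion.

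Section 2.2 defines the three measures:

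- Target lesion: "Time to loss of Assisted Primary Patency of the target lesion is defined as time following study procedure until uncorrectable target lesion occlusion".
- Circuit: assisted patency is "defined as the time following initial study procedure until complete access abandonment".
- IPF: time to access abandonment "divided by number of venous outflow circuit re-interventions to maintain hemodialysis", reported at 3, 6 and 12 months.

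Two further measures respond to obstructions but are not cited in the reason. Target Lesion Primary Patency at 30 days is the primary effectiveness endpoint and ends at the next target lesion intervention or at uncorrectable occlusion. The other is listed in Section 2.2 as "Proportion of subjects with Primary Patency of the venous outflow circuit at 30 days, 3, 6, and 12months" and ends at the next circuit intervention.

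**The concern.** The exclusion has no exception for seriousness. An obstruction that puts a subject in hospital or in surgery within 30 days meets the endpoint's own outcome criteria, yet it is left out because it is said to be captured elsewhere. If the other measures record only that an intervention took place, its seriousness is lost. Lost Primary Patency looks the same for an outpatient balloon re-intervention as for an obstruction that needed surgery or admission.

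Section 4 describes a first-in-human study, and Section 9 plans summaries with confidence intervals and no comparisons. The reported proportions are therefore the safety result. What is at stake is whether a reader of the specified outputs can tell how many early obstructions were serious.

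**Working it through.** The plan gives no figure to reproduce: Section 9 justifies approximately 50 subjects without a rate, margin or formula. The check is a trace through the definitions, followed by a short illustration.

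**Trace.** Take an obstruction by day 30 that leads to surgery or hospitalization and is corrected with the access kept.

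| Output | Source | Result |
|---|---|---|
| Primary safety endpoint | 2.1, 4, 9 | Not counted |
| AE | 7.1 | No |
| SAE | 7.1 | No, since an SAE must be an AE |
| Procedure or device related AEs at 3, 6 and 12 months | 2.2 | Not counted |
| Assisted Primary Patency, target lesion | 2.2 | Still patent; no uncorrectable occlusion |
| Assisted Primary Patency, circuit | 2.2 | Still patent; access not abandoned |
| IPF | 2.2 | One more re-intervention, ungraded, first reported at 3 months |
| Target lesion or circuit Primary Patency | 2.1, 2.2 | Failure once an intervention is done; seriousness not recorded |

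If the obstruction is not corrected, it ends an assisted endpoint at uncorrectable target lesion occlusion or access abandonment. Any surgery, hospitalization or death resulting from it is still outside the safety endpoint.

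The stated reason therefore holds for corrected obstructions through IPF alone, and only as a count. It holds for uncorrected ones as a patency loss. In neither case is the serious outcome reported.

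**Illustration.** Assumptions: n = 50 in the Safety Population, no other safety events, and k such obstructions in k different subjects. Intervals are exact (Clopper-Pearson) 95%.

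- As written, for any k: 50/50 = 100%. Lower limit = 0.025^(1/50) = 0.929, so 92.9 to 100.
- Counting k = 1: 49/50 = 98%, interval 89.4 to 99.9.
- Counting k = 2: 48/50 = 96%, interval 86.3 to 99.5.

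The upper limit for the event rate is 100 minus the lower limit above: 7.1% as written, 10.6% with one event counted and 13.7% with two.

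**The case against.** The exclusion is deliberate, open and consistent across four sections. The plan says the three measures capture obstructions; it does not say that each one captures every case or that seriousness is graded. IPF counts every circuit re-intervention from the initial procedure, so a corrected obstruction on day 20 is in the 3-month value. If it lies at the target lesion, it also fails the primary effectiveness endpoint. Section 8 has the Data Monitoring/Clinical Events Committee (DMC/CEC) adjudicate all target lesion and access circuit interventions. The definition of an unanticipated adverse device effect (UADE) is not limited to AEs. Section 5 collects procedure type at additional visits, and Section 12 seeks revisions done at other facilities. Separate clinical consequences of an obstruction can still be recorded as AEs.

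Most of this stands. A reader might infer that corrected obstructions vanish from the study or are concealed; the documents do not support that. Nor can one say that the case report form lacks a hospitalization item, or what the DMC/CEC charter contains, because neither is in the documents. What survives is narrower: no endpoint or summary specified in the documents draws on adjudication, UADE reports or procedure type to say how many obstructions led to surgery, hospitalization or death by day 30.

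A reader might also try to size the problem from the background. Section 1.3 says of a 42-subject central-vein cohort: "Primary patency rates at 3, 6, 12, and 24 months were 97%, 81%, 67%, and 45%, respectively". Assisted patency was 100% at 3 and 6 months. That contrast cannot demonstrate the gap here, because the cohort's definition of assisted patency is not given; the Section 2.2 definitions establish it alone. Nor do these rates give a 30-day frequency. They are losses of any kind at later times, and no share leading to surgery or admission is stated. Working back to day 30 from these rates, or from the pivotal graft trial's 6-month result in Section 1.2 ("TAPP: 51% vs 23%, p<.001"), would need a constant hazard. The cohort's own figures contradict one: the cumulative hazard is -ln(0.97) = 0.030 over the first three months and -ln(0.81/0.97) = 0.180 over the next three, about six times as much.

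**Conclusion.** The point holds as a gap in reporting and in the stated reason, and it should be fixed. Neither assisted endpoint registers a corrected obstruction, and the measures that do register it do not record seriousness. Followed exactly, the plan can report 100% freedom from safety events even though obstructions met the endpoint's own outcome criteria. With 50 subjects, one or two such events would move the estimate by 2 or 4 percentage points and the lower confidence limit by 3.5 or 6.6 points (92.9 to 89.4 or 86.3).

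The trace rests on the plan's definitions alone. The illustration rests on assumed counts, and the documents do not allow the frequency to be estimated. No test or decision rule changes, and the primary safety endpoint is not invalid as defined. What changes is the completeness of the 30-day safety picture.

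**What to change.** 1. Keep the primary safety endpoint. Beside it, in the Safety Population and with an exact 95% CI, report a supplementary 30-day proportion that also counts venous outflow obstructions resulting in surgery, hospitalization or death.
2. Build it from the procedure type and adjudicated interventions already collected. Add a hospitalization item per intervention if the case report form lacks one, cover interventions at other facilities, and state the number of cases with unknown status.
3. In Sections 2.1, 4, 7.1 and 9, correct the stated reason so that it cites Target Lesion and circuit Primary Patency, which do register corrected obstructions.
4. Separately, the sponsor should reconcile the Section 7.1 exclusion with Sections 7.3 and 8, where reporting and DMC/CEC review depend on SAE or UADE status. No reporting or stopping rule is proposed here.

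The cost is at most one data item per adjudicated intervention, one table row and some wording. The supplementary figure may look less favourable than the primary one. The 12-month visit window has already been widened for COVID-19, which suggests that many subjects are past day 30, so hospitalization data may have to be collected retrospectively and may be incomplete.
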